4.1.4 Determination of Treatment Failures

The site investigator first makes the initial determination of treatment success or failure based on the pre-defined study definitions. The site investigator's assessment will be provided to the EAC for blinded, independent adjudication of treatment outcome that will be utilized for study analysis and reporting purposes. This may be done on an on-going basis or a single meeting as deemed appropriate.

4.2 Blinding

Subjects, site personnel, the Data and Safety Monitoring Board (DSMB), EAC, and the Medical Monitor are initially blinded to the randomization assignment. Blinding will be maintained through the data cutoff for the primary efficacy analysis after which the blind will be lifted for the DSMB. The DSMB may be unblinded to individual assignments earlier as needed to adjudicate certain adverse events. Individual randomization assignments will not be revealed to

the subjects, site personnel, EAC or the Medical Monitor until the study is completed. Sites will be provided an emergency unblinding code if it becomes medically necessary to know the treatment group assigned for a particular subject.

Subjects will be randomized to receive either RBX2660 or placebo through an Interactive Response Technology (IRT) System prior to receiving the first assigned blinded study treatment. Randomization assignment is revealed to Rebiotix Operations Department personnel for product preparation and shipment. The Rebiotix Kit is shipped to the site in a sealed carton that is only opened by the IP administrator at the time of administration, out of view of the subject and other site personnel. While the IP administrator will not have access to the actual randomization assignment, it may be possible to guess through visualization at the time of enema preparation and administration. Additionally, subjects will be instructed to disregard any product characteristics that may become evident during or after administration such as the presence or absence of color or odor. To limit study bias, the IP administrator is not allowed to perform any of the subject study assessments.

4.3 Method of Assignment of Subjects to Treatment Arms

After enrollment and confirmation of inclusion/exclusion criteria compliance, randomization occurs via the study database with blinded treatment occurring within 14 calendar days of randomization. The randomization assignment is transmitted only to the Rebiotix Operations Department, who will ship the correct IP to the site for each treatment. Subjects are considered enrolled once they sign the informed consent form.

Trained and authorized study personnel will access the centralized randomization system to randomize the subject to one of the available treatment arms. The randomization schedule will be created using randomized blocks within four strata based on antibiotics used at screening (Vancomycin alone, Vancomycin in combination, Fidaxomicin or Other), and randomized subjects will be assigned one of two treatments (Group A or Group B) within the appropriate

stratum. The randomization will not be stratified by site, so each site will draw from the same set of blocks. A subject will be assigned the next available treatment allocation from the randomization list. The randomization code and the date and time of randomization will be captured in the clinical database. Randomization will be in a 2:1 ratio with approximately 2 subjects randomized to active treatment for every 1 subject randomized to placebo.

Enrolled subjects who are exited prior to randomization or are randomized but exited prior to attempting the blinded treatment may be re-enrolled and thus randomized under a different subject identification numbers (re-randomized). If this occurs, they will be included in the analysis using their second randomization assignment and subsequent assessments and will only be counted once towards the total number randomized.

4.4 Determination of Sample Size

To demonstrate a 69% success with one dose of the RBX2660 treatment group vs. 47% success in the Placebo control group, 240 subjects are required (power > 90%, nominal 2.5% type I error rate). Up to an additional 30 subjects will be enrolled to allow for a 10% loss-to-follow up rate, for a total of approximately 270 subjects. Considering the 2:1 randomization, this results in approximately 180 subjects in the RBX2660 arm and 90 subjects in the Placebo arm. Enrolled subjects who have signed consent and withdraw for any reason prior to administration of the first blinded enema will be replaced without counting toward the sample size cap. Replacement subjects will be randomized to ensure proper blinding.

4.5 Interim Sample Size Re-estimation

There are no plans for an interim sample size re-estimation being completed for this study.

4.6 Randomized Treatment Arms

Placebo Arm – Group A

- Placebo dosing consists of one enema of placebo given in a blinded manner.

RBX2660 Arm – Group B

- Active treatment consists of one enema of RBX2660 given in a blinded manner.

5 CHANGES IN THE CONDUCT OF THE STUDY OR PLANNED ANALYSES

5.1 Changes in the Conduct of the Study

There have been no changes to the conduct of the study or planned analysis.

6 BASELINE, EFFICACY AND SAFETY EVALUATIONS

6.1 Schedule of Events

Activity	Screening (Enrollment)	Baseline / Enema Administration (≤21 days from screening)	Follow-up Visits 1-, 4- and 8- Week (± 3 days) Assessments ¹	Weekly Phone Assessment (Weeks 2, 3 and 6, (± 3 days)	Unscheduled Possible Recurrence Visit	Unblinded Enema Administration ¹ (≤10 calendar days from Tx Failure)	Phone Assessment at 3 and 6 months (± 14 days)
Informed consent obtained	X						
Demographics, medical history	X						
Prescribe/continue antibiotics for CDI symptom control	X						
Modified physical exam conducted		X					
Stool sent to Rebiotix by subjects for testing and archiving (optional)	X		X		X		X
Central Lab CBC w/differential testing ³	X ³	X					
Central Lab CMP & CRP testing	X						
C. difficile testing ⁴	X ⁴				X ⁴		
Central Lab stool and blood testing		X					
Urine pregnancy testing performed at site (if applicable)	X	X				X	
Cdiff32 Questionnaire	X		X		X		X
Inclusion/exclusion criteria confirmed	X	X					
Randomization assignment	X ⁵						
24-72hr washout period confirmed		X				X	
Enema administered		X				X	
Product complaint (if applicable)		X				X	
Recurrence or New CDI symptoms assessed		X	X	X	X	X	X
Vital signs assessed	X	X			X	X	
Subject Diary discussed/reviewed	X	X	X ⁶			X	
Employment status assessed	X		X ⁷				X
Concomitant medications	X	X	X	X	X	X	X
Medical History Assessment	X		X ⁷		X		X
Adverse events assessed		X	X	X	X	X	X
Solicited events assessed ²		X	X ²			X ²	
Protocol deviations (if applicable)	X	X	X	X	X	X	X

¹ Documented treatment failures may receive an unblinded RBX2660 enema. If an unblinded enema is administered, the follow-up visit requirement re-start based on the date of last enema administration.

² Solicited events are collected in the Subject Diary from the day of administration of any study enema (blinded or unblinded) until the day prior to the 1-week visit. The Subject Diary is collected and reviewed at the 1-week visit. Solicited events that increase in severity from screening should be assessed for a possible adverse event.

³ Exclusion criteria for absolute neutrophil count should be assessed based on the CBC collected at the screening visit.

⁴ Perform within 30 days prior to or at enrollment and if CDI recurrence is suspected.

⁵ Randomization should occur after screening criteria has been assessed and eligibility confirmed (4-14 calendar days from randomization to blinded study treatment)

⁶ Subject Diary is reviewed only at the 1 week follow-up visit

⁷ Collected at the 8 week follow-up visit only.

6.2 Time Point Algorithms

6.2.1 Relative Day

The date of study enema administration will be considered relative day 1, and the day before study enema administration will be relative day -1. Relative days will be calculated as follows only when the full assessment date is known (i.e., partial dates will have missing relative days, unless imputation methods have been specified):

For days before first enema:

Date of Assessment – Date of first enema administration

For days on or after first enema:

Date of Assessment – Date of first enema administration +1

6.2.2 Windows

For the purpose of statistical analysis, the analysis visit windows will be calculated in terms of study days since the day of the study enema administration, as illustrated in the following tables:

Analysis Windows for Clinical Visits

Visit	Scheduled Study Day	Visit Window in Protocol (Days)	Visit Window for Analysis (Days)
Screening Visit	-30 through -1	-30 through -1	-30 through -10
Baseline/1 st Enema	1	1	1
Week 1 Office	8	5 - 11	5 - 11
Week 4 Office	29	26 - 32	26 - 32
Week 8 Office	57	54 - 60	54 - 60

Analysis Windows for Phone Assessments

Visit	Scheduled Study Day	Visit Window in Protocol (Days)	Visit Window for Analysis (Days)
Week 2 - Phone	15	12 - 18	12 - 18
Week 3 - Phone	22	19 - 25	19 - 25
Week 6 - Phone	43	40 - 46	40 - 46
3 month - Phone	90	76 - 104	76 - 104
6 month - Phone	180	166 - 194	166 - 194

If a subject has more than one assessment occurring in the same visit window, the data from the visit closest to the scheduled study day will be used for analysis. If two visits have the same distance from the scheduled study day, i.e., one visit occurs -1 day from study day, and the other visit occurs +1 day from study day, the data from the visit after the scheduled study day will be used for analysis.

Analysis Windows for Adverse Event Reporting by Onset Interval

Onset Interval Name	Onset Interval Analysis Window	Window for Analysis (Days)
Baseline	Screening - < Baseline	≤ -1
1-week	Baseline - 1-week	1 through 8
4-week	> 1-week - 4-week	9 through 29
8-week	> 4-week - 8-week	30 through 57
4-month	> 8-week - 4-month	58 through 121
6-month	> 4-month - 6-month	122 through 180+

6.3 Analysis Populations

The modified Intent-to-Treat will be analysis of import for the primary endpoint.

6.3.1 Intent-to-Treat Population

Analysis of the primary efficacy endpoint will be done using the Intent-to-Treat (ITT) population as a sensitivity analysis. The ITT population is defined as all randomized subjects. Subjects will be analyzed according to the randomized treatment rather than the actual treatment received regardless of treatment misallocations. Re-randomized subjects will be summarized using their second treatment assignment (see Section 4.3 for details). Randomized subjects who exited prior

to receiving blinded treatment will not be included in the analysis. Randomized subjects in whom blinded treatment was attempted but delivery of the enema was not successful will be counted as treatment failures. Randomized and treated subjects who exited prior to their 8-week efficacy assessment will be counted as treatment failures even if protocol required treatment failure documentation is not on file. Additionally, the secondary efficacy endpoints may be evaluated using the ITT population.

6.3.2 Modified Intent-to-Treat Population

For the Modified Intent-to-Treat (mITT) population, subjects will be analyzed according to the randomized treatment assignment despite any treatment misallocations.

Additionally, the mITT population will be defined as all randomized subjects who successfully received blinded treatment but excluding;

- subjects who withdrew prior to treatment;
- subjects in whom treatment was attempted but not completed and;
- subjects who discontinue from the study prior to evaluation of treatment failure/success for the primary endpoint if the reason for exit is not related to CDI symptoms. Reason for exit will be captured on the exit form to allow for identification of such subjects.

Examples of reasons unrelated to CDI symptoms may include;

- Withdrawal of consent
- Death unrelated to CDI

Subjects who were exited prior to the 8-week efficacy assessment due to CDI related symptoms will be counted as treatment failures even if documentation as required per the protocol is not on file for the treatment failure.

The mITT population will be used for the primary efficacy reporting purposes. The mITT population will also be used for secondary and exploratory endpoints evaluation. The analysis of the ITT and PP populations may also be provided in addition to the mITT for purposes of regulatory evaluation.

6.3.3 Per-Protocol Population

The per-protocol (PP) population will consist of all subjects who successfully received blinded treatment analyzed according to the treatment they received, excluding;

- Subjects who have documented deviations to inclusion or exclusion criteria.
- Subjects who exited prior to the 8-week efficacy evaluation if the reason for exit was not related to CDI symptoms in the same manner as the mITT population.

The primary, secondary and exploratory endpoints will be evaluated using the PP population.

6.3.4 Safety Population

The safety population (SP) will be defined as the population of randomized subjects who had any blinded treatment attempted or completed. Subjects will be analyzed according to the treatment they actually received should misallocations occur. The safety population will be used in analysis of all safety endpoints.

6.4 Efficacy Variables

6.4.1 Primary Efficacy Endpoint

The primary efficacy endpoint is the recurrence of CDI within 8 weeks of blinded treatment. The primary analysis of the study will be a Bayesian hierarchical model, which formally incorporates data from a previous randomized Phase 2B study (Protocol 2014-01) of RBX2660. This analysis will demonstrate the efficacy of RBX2660 by showing a sufficiently high posterior probability that the rate of success in the treatment group is superior to the rate of success in the control group.

6.4.2 Secondary Efficacy Endpoint

The secondary efficacy endpoint is the recurrence of CDI through 6 months after blinded treatment. This will be analyzed as the difference in time to CDI event between RBX2660 and Placebo following blinded treatment through 6 months of follow-up. This analysis will only be

analyzed if statistical significance ($p < 0.05$) is demonstrated for the primary efficacy endpoint. These endpoints will be tested at a two-sided 0.05 significance level.

The null hypothesis of interest is that there is no difference between RBX2660 and Placebo treated subjects in the probability of CDI at any time point during the 6 months of follow-up. The alternative is that there is a difference in the probability of CDI at any time point during 6 months of follow-up.

The power to detect the difference between RBX2660 and Placebo treatment at 6 months was estimated by 10,000 simulations of time to event data, with 104 subjects per treatment group. The data was simulated assuming the exponential distribution with the rate parameter lambda estimated using the 8-week success rates of 69% and 47% for RBX2660 and Placebo, respectively. Using the log-rank test, the power to detect the difference between the two groups at 6 months was 99.5%.

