7.6 Analysis of Efficacy

7.6.1 *Analyses Supporting the Primary Efficacy Endpoint*

7.6.1.1 *Treatment Success*

A hierarchical, closed-testing procedure will be utilized for the primary endpoint and secondary endpoints. Analyses of the single primary endpoint, recurrence of CDI within 8 weeks of blinded treatment, will be analyzed as the proportion of treatment success of Group A Placebo (P_{PLA}) and Group B RBX2660 (P_{RBX}). This analysis will be performed on the ITT, mITT and PP populations, with the mITT being the analysis of import for reporting purposes.

The primary efficacy analysis will be a Bayesian hierarchical model which formally incorporates data from the previous Phase 2B study (Protocol 2014-01) of RBX2660. Study success will be declared if the posterior probability of superiority exceeds 0.99943 at the first two interim analysis. If the trial continues to the maximum enrollment, the success criteria will be chosen so that the overall alpha is a nominal 0.00125. Success at this level is considered appropriate for approval based on results from a single study. If success at this level is not met at the final analysis, success may also be declared if the posterior probability exceeds 0.97706. Success at this secondary threshold still constitutes a successful study, although it may not be sufficiently strong evidence to request regulatory approval based on a single study without further FDA discussion. Details regarding the analysis can be found in Section 10 (Bayesian Analysis Plan).

The secondary endpoints will be analyzed using a hierarchical testing approach if sufficient evidence is found to claim study success.

The primary efficacy analysis will be conducted when all subjects in each group reach their 8-week assessment following blinded treatment or early termed from the study. Full study results in the form of a final analysis and report will be completed once the last subject has completed the 6-month telephone assessment, at which time the study will be considered complete. This includes subjects receiving unblinded RBX2660 due to a documented treatment failure.

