7.6.2 Analysis Secondary Efficacy Endpoint

A hierarchical, closed-testing procedure will be utilized for the secondary endpoint: If the null hypothesis for the primary efficacy endpoint is rejected, the secondary endpoint will be analyzed. The secondary endpoint will be tested at a two-sided 0.05 significance level.

7.6.2.1 Sustained clinical response of RBX2660 vs. Placebo.

The null hypothesis of interest is that the rates of sustained clinical response (i.e., the rate of CDI occurrence with treatment success of the presenting CDI recurrence and no new CDI episodes for greater than 8 weeks after completing a blinded study treatment) are the same between the RBX2660 group and the Placebo group during the 6 months of follow-up. The alternative is that there is a difference in sustained clinical response rates. A Pearson's chi-square test will be used to test the null hypothesis that the response rate in the treatment group is equal to that of the control group. In addition, two-sided 95% confidence intervals for the difference in response rate between arms will be calculated using a normal distribution approximation. The null hypothesis will be rejected at the two-sided 0.05 significance level. Subjects who were deemed a Treatment Success for the efficacy analysis and exited prior to their 6 month follow-up will be conservatively counted as a sustained treatment failure for the purpose of this analysis.

An analysis of time to CDI occurrence after completion of the assigned blinded treatment will be analyzed and presented by the Kaplan-Meier procedure and median duration presented by days (and weeks) using the ITT, mITT, and PP populations. The estimates will be presented for each of the time points at which CDI recurrence assessments are scheduled to occur. A graphic presentation of the Kaplan-Meier estimates will supplement the tabular presentation. Between group comparisons will be performed using the log-rank test.

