Time to CDI occurrence is defined as the number of days from enema administration to first assessment indicating recurrence, for those subjects who were deemed Treatment Failures or Indeterminate. Randomized subjects who do not complete the assigned blinded treatment will be censored at Day 0. All subjects who are discontinued for any reason prior to the 6-month timepoint will be censored at the last assessment date at/prior to Month 6. All subjects considered as a sustained treatment success will be censored at the date of their 6-month assessment.

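### The only gated secondary endpoint has two different tests at two-sided 0.05, and neither the SAP nor the protocol says which one decides

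*SAP*

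**What the plan says.** SAP 6.4.2 defines the single secondary endpoint as CDI recurrence through 6 months after blinded treatment and continues: "This will be analyzed as the difference in time to CDI event between RBX2660 and Placebo following blinded treatment through 6 months of follow-up". Its null hypothesis is "no difference between RBX2660 and Placebo treated subjects in the probability of CDI at any time point during the 6 months of follow-up", and it sets the level: "These endpoints will be tested at a two-sided 0.05 significance level". It reports 99.5% power for a log-rank test, from 10,000 simulations with 104 subjects per group and exponential times fitted to 8-week success of 69% and 47%.

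SAP 7.6.2.1 gives the same endpoint a different null, that sustained clinical response rates are equal: "A Pearson's chi-square test will be used to test the null hypothesis that the response rate in the treatment group is equal" to that of control, and "The null hypothesis will be rejected at the two-sided 0.05 significance level". Week-8 successes who "exited prior to their 6 month follow-up will be conservatively counted as a sustained treatment failure". The section then adds a Kaplan-Meier analysis with a log-rank comparison. It does not call this supportive, and its exit rule is the opposite one: "All subjects who are discontinued for any reason prior to the 6-month timepoint will be censored at the last assessment date".

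On ordering, SAP 7.6.1.1 says only: "The secondary endpoints will be analyzed using a hierarchical testing approach if sufficient evidence is found to claim study success". SAP 8.7 refers back to 7.6.1.1. Protocol 2.2, 2.5 and 8.1 name no test for this endpoint.

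SAP 7.6.1.2 also describes time to recurrence through 6 months, with a log-rank test stratified by the randomization factor.

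**The concern.** A closed procedure needs one prespecified test for each hypothesis it passes to. Here the second step has two complete specifications, each with its own null hypothesis and its own rejection level. If the primary succeeds and the two tests disagree, both a positive and a negative secondary claim could be defended from the SAP's text, and the choice would be made after the results are known.

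The two tests also ask different questions. One compares the whole course of CDI over 6 months and drops early leavers from the risk set. The other compares a status at 6 months and counts early leavers as failures. Either treatment of leavers is acceptable within its own analysis. The fault is that the deciding analysis is not named.

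**Working it through.** **1. The two specifications side by side**

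| | SAP 6.4.2 | SAP 7.6.2.1 |
|---|---|---|
| Null | No difference in probability of CDI at any time through 6 months | Equal sustained response rates |
| Test | Time to event; log-rank in the power sentence | Pearson's chi-square |
| Level | Two-sided 0.05 | Two-sided 0.05 |
| Week-8 success who exits before month 6 | Censored (rule given in 7.6.2.1) | Failure |
| Stated power | 99.5% | None |

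**2. The plan's own figure reproduces**

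- Hazards: −ln(0.69)/56 and −ln(0.47)/56 per day, so HR = ln 0.69 / ln 0.47 = 0.491.
- CDI-free at day 180: 0.69^(180/56) = 0.303 and 0.47^(180/56) = 0.088.
- Expected events at 104 per group: 104 × 0.697 + 104 × 0.912 ≈ 167.3.
- Schoenfeld power: Φ(√(167.3 × 0.25) × |ln 0.491| − 1.96) = 99.6%. A 10,000-run log-rank simulation gives 99.5%.

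The trial randomizes 2:1. With the same hazards, Schoenfeld power is 99.5% at 160/80 and 99.8% at 180/90, so the 1:1 assumption hardly matters. The constant hazard does. It implies that only 0.303/0.69 = 44% of RBX2660 week-8 successes remain CDI-free at day 180, and 0.088/0.47 = 19% on placebo. Protocol 1.5.2 reports a crude long-term CDI-free rate of 95.8% (91/95) among RBX2660 successes in Study 2014-01.

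**3. Power of each test when late recurrence is less common**

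Assumptions: 69% vs 47% at day 56, the stated share of week-8 successes CDI-free at day 180 (durability), and late exits spread evenly over days 56–180. The documents give no exit rate for this period and no placebo durability, so both are shown as ranges.

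Hand check at 160/80, 95.8% durability in both arms, 10% late exits:

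- Chi-square success rates: 0.69 × 0.958 × 0.9 = 0.595 and 0.47 × 0.958 × 0.9 = 0.405, a difference of 0.190.
- Pooled rate 0.532; null SE = √(0.249 × (1/160 + 1/80)) = 0.0683; unpooled SE = 0.0672.
- Power ≈ Φ((0.190 − 1.96 × 0.0683)/0.0672) ≈ 80%. Exact enumeration gives 79.5%.

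Exact chi-square power at 0/5/10% late exits, and simulated log-rank power over the same exits:

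| Durability RBX2660/placebo | Chi-square 160/80 | Chi-square 180/90 | Log-rank 160/80 | Log-rank 180/90 |
|---|---|---|---|---|
| 95.8/95.8% | 87.8/83.8/79.5 | 91.3/88.2/84.6 | 90.6–90.9 | 93.1–93.6 |
| 95.8/90% | 94.2/91.5/88.4 | 96.3/94.5/92.1 | 94.5–95.1 | 96.6–97.0 |
| 95.8/80% | 98.8/98.0/96.7 | 99.5/99.0/98.2 | 98.6–98.9 | 99.2–99.3 |

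**4. How often the two tests disagree**

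There were 10,000 simulated trials per scenario, counting only those that pass the primary gate (98–99% do). The gate is the SAP's hierarchical model with 2014-01 groups B (19/44) and C (25/42), in a normal approximation, with posterior above 0.97706 at the final analysis only. Against SAP Table 4, which includes the interims, at control rate 0.45 it gives 0.034 vs 0.042 for effect 0, 0.823 vs 0.833 for 0.15, and 0.967 vs 0.969 for 0.20.

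Percentage of gated trials with opposite decisions (160/80; 180/90):

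| Durability RBX2660/placebo | No late exits | 5% | 10% |
|---|---|---|---|
| 95.8/95.8% | 3.2; 2.7 | 8.9; 6.1 | 13.1; 10.3 |
| 95.8/90% | 1.5; 1.0 | 4.4; 2.7 | 7.9; 5.5 |
| 95.8/80% | 0.3; 0.2 | 0.8; 0.5 | 1.9; 1.3 |

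In the top row at 10% exits, 12.3 of the 13.1 points and 9.6 of the 10.3 are trials where log-rank is significant and chi-square is not.

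Under the SAP's own constant hazard, ungated disagreement is smaller: 1.3% at 160/80 and 0.7% at 180/90 with no exits, and 3.1% and 1.7% with 10%.

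**5. Error rate if either test may be claimed**

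With no true difference, 160/80 and no dropout, each test alone rejects in about 5% of trials (log-rank 5.1–5.4%, chi-square 4.6–5.0%). Claiming whichever is significant rejects in 6.7–8.0%.

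**6. The 6-month time-to-event analysis has two descriptions**

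SAP 7.6.1.2 stratifies the log-rank test and censors Indeterminate subjects, in wording written mainly for week 8 but followed by a 6-month sentence. SAP 7.6.2.1 does not mention stratification and gives Indeterminate subjects an event time. Neither event definition says outright that CDI after week 8 counts. It sensibly should.

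**The case against.** The best reply is that 7.6.2.1 governs. It sits in the analysis section, ties one null, one test, one rejection rule and one conservative exit rule to sustained clinical response, and fits the objective's wording about a response rate. Section 6.4.2 is under efficacy variables and names log-rank only when giving power. The Kaplan-Meier paragraph in 7.6.2.1 has no null or level of its own. This reading is plausible, but it is an inference. It leaves the null, the level and the statement of analysis in 6.4.2 without effect, and it leaves the chosen test with no stated power.

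The objection on size partly stands. The 10–13% needs assumed late exits and 95.8% durability in both arms. That 95.8% is a crude figure for RBX2660 successes in another study, at a mean of 8.2 months (range 1.6–14.9), and nothing supports it for placebo. Under the SAP's own hazard, disagreement is a few percent at most. Disagreement is also not itself an error rate, which is why step 5 is shown.

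The gate also ignores early stopping at the interims. An approximation that includes them gives about 2.6%, 6.0% and 11.7% at 0, 5 and 10% exits with 95.8% durability in both arms, so the conclusion is unchanged.

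Finally, both analyses can be run as written; what is missing is the rule for which one decides. The points on stratification, Indeterminate subjects and the 104-per-group input are minor, and the severity does not rest on them.

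**Conclusion.** The concern holds. SAP 6.4.2 and 7.6.2.1 give conflicting confirmatory rules for one endpoint, and no section resolves them. This follows from the text alone and must be fixed before unblinding.

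The practical size depends on late exits and durability, which the documents do not supply. Opposite conclusions arise in 0.2% to 13.1% of gated trials over the scenarios examined, mostly in the direction where log-rank succeeds and chi-square does not. The stated 99.5% is correct arithmetic for a log-rank test under a constant 8-week hazard. It does not describe the chi-square test, whose power at 2:1 runs from about 80% to above 99% over the same scenarios.

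The primary endpoint, sample size and success thresholds are unaffected.

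**What to change.** Before any unblinding by arm:

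- Name one confirmatory test, with one null hypothesis, in both 6.4.2 and 7.6.2.1, and label the other supportive. Either is acceptable. Chi-square on sustained clinical response is one option that fits Protocol 2.5.
- Give the 6-month time-to-event analysis a single specification in 7.6.1.2 and 7.6.2.1. State whether it is stratified, handle Indeterminate subjects one way, and define an event as any CDI episode through 6 months, including after week 8.
- Restate power at 2:1 for the named test, as a range over stated 6-month rates per arm and stated exit rates.

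The cost is SAP wording and one recomputed power range. No patients, visits or data are added.
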